The European feasibility trial of the CARILLON Mitral Contour System, named TITAN, is a multi-center, safety study for the treatment of functional mitral regurgitation. The primary objective of the study is to evaluate the safety of deploying and implanting the CARILLON device in the coronary sinus/great cardiac vein in patients with functional mitral regurgitation. The secondary objectives are to determine the long-term safety of the device, and the effect of the device on hemodynamics and patient function.

The TITAN Trial Investigational Plan was reviewed and approved by the appropriate medical ethics committees and notification was made to the Competent Authorities. The TITAN Trial was initiated in April 2008. Three (3) sites in Germany, two (2) sites in Poland, and two (2) sites in France were ultimately initiated.

Patients with dilated ischemic or non-ischemic cardiomyopathy, moderate to severe FMR, ejection fraction < 40%, and six minute walk distance between 150 and 450 meters were enrolled in the TITAN Trial. Echocardiographic FMR grade, exercise tolerance, NYHA class, and Quality-of-Life (QOL) were assessed at baseline, one, six and twelve months. Of the 65 subjects enrolled in the trial, 12 subjects did not meet the study eligibility criteria. Of the 53 subjects who underwent a procedure to implant the CARILLON device, 36 ultimately received the CARILLON device. Seventeen subjects did not receive a device due to access issues, insufficient acute FMR reduction, or coronary artery compromise.

The major adverse event rate was 1.9% at 30 days. Analysis of the TITAN study indicates that at 12 months, the degree of FMR reduction among four different quantitative echo measures ranged from 32 – 46%, with regurgitant volume showing a the greatest reduction between baseline and 12 months. NYHA grade improved by 32% from baseline to 12 months, six minute walk distance improved by over 125 meters (41% increase from baseline) and QOL, as measured by the Kansas City Cardiomyopathy Questionnaire, improved by 53% at twelve months. Left ventricular dimensions in the implanted population also showed a significant trend toward reverse remodeling, with end diastolic and systolic volumes decreasing by 9% and 12%, respectively at 12 months. The results of the TITAN study have been published in a peer-reviewed journal - European J. Heart Failure in 2012.³¹

[figure not shown]
1.3.6.3 Safety Study of the CARILLON Mitral Contour System, Europe – The TITAN II Trial:

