2.2 Principles of Operation

The CARILLON implant is implanted through transvenous placement (jugular cannulation) under fluoroscopy following standard percutaneous cannulation/ catheterization procedures.

After catheterization of the coronary venous system, an assessment of the size of the CS/GCV is made to determine the proper sizing of the CARILLON implant. This is accomplished by performing a venogram to assist in measurement of vein diameter and length. An angiogram is also performed to determine the location of the coronary arteries in relation to the CS/GCV.

The CARILLON implant is comprised of distal and proximal anchors joined with a ribbon connector. The design of the distal portion of the implant (described as the “distal anchor”) enables it to be anchored in the distal portion of the GCV. This is accomplished by expanding the anchor in the vein and locking it in place with the tip of the delivery catheter. The pressure applied on the vein wall by the expanded and locked anchor enables secure anchoring of the CARILLON implant. The delivery catheter is then withdrawn proximally to expose the ribbon connector.

Tension is applied manually to the delivery system, pulling the proximal portion of the CARILLON implant (described as the “proximal anchor”) toward the CS ostium. Fluoroscopy and echocardiography guide the tensioning process. The proximal anchor is deployed and locked in the CS by advancing the sheath component of the delivery system, thus reshaping the mitral annulus. After determining that no coronary artery flow is compromised (assessed by coronary angiography), that there is some reduction

in the mitral regurgitation characteristics (assessed by echocardiography) and ensuring that the proximal anchor is locked (assessed by fluoroscopic imaging), the operator may then decouple the handle assembly from the implant and remove the catheter.

[figure not shown]

Figure 2.4 Deployment of the CARILLON Implant and Plication of the Mitral Valve Annulus

The CARILLON Mitral Contour System is designed to enable acute recapture during the implantation procedure (prior to decoupling) if for any reason the implant cannot be successfully deployed, or for other clinical or safety reasons. The implant is recaptured by advancing the sheath to the proximal anchor arrowhead. The delivery catheter is then advanced over both the proximal and distal anchors by turning the control knob. Both anchors will be completely recaptured into the delivery catheter

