- Hypothesized mean regurgitant volume change (baseline to 12-month) in the Control group = -2.4 ml
- Hypothesized mean regurgitant volume change (baseline to 12-month) in the Treatment group = -12.4 ml
- Hypothesized standard deviation:

- Treatment group = 13 ml,
- Control group = 13 ml
- 3:1 randomization allocation

Under the assumptions outlined above, the estimated minimum required sample size is 76 subjects (57 Treatment, 19 Control).

Justification for Sample Size Assumptions

Assumptions for sample size calculations are derived from a two previous studies of subjects implanted with the CARILLON Mitral Contour System in a similar patient population – the TITAN and TITAN II studies. The hypothesized mean change (baseline to 12 months) for the Control group is conservatively assumed to be approximately -2.4 ml. The hypothesized mean change for the Treatment group, and the standard deviations for both groups, is expected to be similar to that observed in the TITAN and TITAN II study cohorts 12 months after implantation. In these studies, the observed change in regurgitant volume at 12 months was -14.1 ml. The observed mean difference between the populations is adjusted to account for as many as 15% of the Treatment group subjects not receiving a permanent implant (Non-Implanted Treatment group patients) but still counted in the intent to treat analysis, thus yielding regurgitant volume results similar to the Control group, without compromising the power of the study. This study assumes a -10 ml mean difference in regurgitant volume between the study populations.

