6.9 Supportive Analyses & Missing Data Imputation

The following supportive analyses will also be undertaken.

- Assessment of treatment efficacy in subjects receiving a permanent implant through the primary endpoint – “as-treated” analysis
- Assessment of treatment efficacy in subjects receiving a permanent implant and who did not receive alternative or confounding therapies (e.g., CRT therapy, transplant, stenting, etc.) through the primary endpoint – “per protocol” analysis
- Assessment of treatment efficacy according to etiology of cardiomyopathy (ischemic vs. non-ischemic) through the primary endpoint
- Assessment of treatment efficacy according to baseline LV ejection fraction ($\leq 40\%$ vs. 41-50%) through the primary endpoint

Missing data will be imputed using a last observation carried forward (LOCF) methodology and be reported separately for:

- the primary and secondary endpoint parameters
- the observational parameters
- the primary (intent to treat) and supportive analyses noted above.

7 **Ethical, Regulatory, and Administrative Considerations**

This study will be conducted in accordance with the International Standard ISO 14155:2011, recommendations guiding physicians in biomedical research involving human subjects adopted by the 18th World Medical Assembly, Helsinki, Finland, 1964 and later revisions, Good Clinical Practice: Consolidated Guidance (ICH E-6) and any regional or national regulations, as appropriate.

Only centers willing and able to comply with these practices will be included in the study.

7.1 **Informed Consent**

To protect the rights and welfare of subjects, this clinical study will be conducted in conformance to the International Standard ISO 14155: 2011, Section 4.7: Informed Consent.

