## STATISTICAL ANALYSIS PLAN

REDUCE\_FMR - SAP\_V2  
2018\_08\_06\_CT

REDUCE FMR Trial

Page 14/22

- Significance level two-sided 0.05;
- Statistical power to detect design alternative hypothesis is 80%;
- Hypothesized mean regurgitant volume change (baseline to 12-month): Control group = -2.4ml; Treatment group = -12.4ml;
- Hypothesized standard deviation: Control group = 13ml; Treatment group = 13ml;
- 3:1 randomization allocation.

Under the assumptions outlined above, the estimated minimum required sample size is 76 subjects (57 Treatment, 19 Control).

A total of 120 subjects at up to 20 centers will be randomized, allowing for approximately 30% attrition (mortality, missing data and loss to follow-up) in the first 12 months of follow-up.

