#### 2.3.2. Definition of patient populations

5 populations will be defined:

- The enrolled population will include all patients who consented to participate to the study.
- The screen failure population will include all enrolled patients who did not meet all eligibility criteria or randomized to treatment group but procedure discontinued before an implant attempt. Only a listing of these patients will be presented.
- The Intent-to-Treat (ITT) population will include all patients who fulfill all eligibility criteria and either underwent the procedure and on whom a device implant was attempted, or are considered as control patients.

This population will therefore include all randomized patients except the patients for whom the procedure was discontinued before an implant attempt (see Fig 1 below).

This population will be analyzed regardless of the treatment actually received: if there is an error in treatment (i.e. subject was not treated as randomized), the analysis will be performed according to the randomized group assignment, not the treatment actually received.

- The As -Treated (AT) population will include all ITT patients who left clinic with the randomized therapy administered (i.e., randomized to Treatment group and received a permanent implant, or randomized to Control group)

This population will therefore include all randomized patients except the patients who underwent the procedure but were not implanted (see Fig 1 below).

This population will be analyzed according to the treatment actually received: if there is an error in treatment (i.e. subject was not treated as randomized), the analysis will be performed according to the treatment actually received, not the randomized group assignment.

- The Per Protocol (PP) population will include all AT patients who received randomized therapy, assessors remained blinded, and who did not receive alternative or confounding therapies (e.g., CRT therapy, transplant, stenting, etc.) through the primary endpoint timeframe of the study, who did not met any major deviation (see 2.3.3).

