### 2.4.2. **Primary Endpoint**

The primary analysis will be performed on the Intent to treat (ITT) population.

The primary efficacy endpoint is to compare the change in regurgitant volume from baseline at 12 months between the treatment and control groups using a two-sided, two-sample t-test (or Wilcoxon Rank sum test as appropriate). The corresponding 95% confidence interval on the between-group difference will also be calculated and presented.

A sensitivity analysis of the primary efficacy endpoint analysis on the ITT population will be performed, using the last observation carried forward (LOCF) missing data imputation on the regurgitant volume at 12 months. The same comparison analysis as mentioned above for the primary efficacy endpoint will be performed.

Two other additional analyses will be performed on the primary efficacy endpoint on:

- As-treated population
- Per-protocol population

The same comparison analysis as for the primary efficacy endpoint mentioned above will be used

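### The as-treated and per-protocol sets drop failed implants from the Treatment arm only, so they are non-randomized comparisons open to selection bias, most likely towards the device

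*SAP*

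**What the plan says.** SAP 2.3.2 takes the as-treated set from the ITT patients who left the clinic with their assigned therapy, and sums up: "This population will therefore include all randomized patients except the patients who underwent the procedure but were not implanted". Controls qualify simply by being Controls. Because the set sits inside the SAP's ITT population, Treatment patients whose procedure stopped before any attempt are missing too, which that sentence does not say. The per-protocol set is a subset of as-treated. Its further exclusions (unblinding, confounding therapy, other major deviations) can fall on either arm.

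Under Protocol 2.2 the operator releases the implant after confirming that coronary flow is intact, that echocardiography shows some fall in MR, and that the anchor is locked. Protocol 1.1 also has efficacy rechecked before release. Controls have no attempt (Protocol 3.7.1.3). For TITAN, Protocol 1.3.6.2 reports: "Seventeen subjects did not receive a device due to access issues, insufficient acute FMR reduction, or coronary artery compromise". AMADEUS gives the same three reasons.

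Protocol 6.9 describes the as-treated analysis as "Assessment of treatment efficacy in subjects receiving a permanent implant through the primary endpoint". For both sets SAP 2.4.2 says: "The same comparison analysis as for the primary efficacy endpoint mentioned above will be used". SAP 2.4.3 extends them to the secondary endpoints. ITT is the primary analysis in both documents.

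Treatment patients with a failed attempt are followed to 12 months, while those with no attempt leave after one month (Protocol 3.7.1.2). Controls are offered the device only after their one-year follow-up (Protocol 3.8.7).

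**The concern.** The exclusion happens after randomization, in one arm only, and on a result that may be related to the outcome. Treatment patients who pass an on-table check are compared with Controls who were never checked. If patients who fail the check would have done worse at 12 months without a device, removing them flatters the Treatment arm even when the device does nothing.

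These two sets are the plan's only estimates of the effect in patients who actually receive an implant. They are tested in the same way as the primary analysis and cover the secondary endpoints. Neither document says that they lose the protection of randomization, and neither plans an estimate that keeps it.

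**Working it through.** **Inputs.** Two-sided 5% test, 80% power, mean changes of -2.4 ml (Control) and -12.4 ml (Treatment), SD 13 ml, 3:1 allocation, 120 randomized with about 30% attrition (SAP 2.2; Protocol 6.6 and 6.7). Change of -14.1 ml in implanted patients and up to 15% non-implants (Protocol 6.6). Non-implants in prior studies: TITAN 17/53 = 32.1%, TITAN II 6/36 = 16.7%, the two pooled 23/89 = 25.8%, AMADEUS 18/48 = 37.5% (Protocol 1.3.6).

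**The plan's own figures.** With the noncentral t distribution, 54 + 18 = 72 patients give 79.6% power and 57 + 19 = 76 give 81.8%, so the stated 76 reproduces. The Treatment mean also reproduces: 0.85 × (-14.1) + 0.15 × (-2.4) = -12.35, close to -12.4.

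**Where bias comes from.** Let p be the non-implant share. Let d be how much worse, in ml and without a device, non-implantable patients do than implantable ones. The Control arm contains both kinds in proportions p and 1 - p, and the as-treated Treatment arm contains only implantable patients. The as-treated difference is therefore shifted towards the device by p × d. The shift is zero if d = 0 and reverses if d < 0.

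On the planning figures, 0.85 × (-14.1 + 2.4) = -9.945 ml for all randomized patients and -9.945/0.85 = -11.7 ml for implanted patients. Removing dilution explains that whole gap, so the gap is not itself evidence of bias.

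**Illustration with no device effect.** Assume the worst on-table fraction f is excluded and the on-table reading has correlation r with the 12-month change. The shift is 13 × r × φ(z_f)/(1 - f), where z_f is the normal quantile at f and φ the normal density. The factor 13 × φ(z_f)/(1 - f) is 3.57 at f = 15%, 3.90 at 16.7% and 5.67 at 25.8%. Evaluable patients: 120 × 0.70 = 84, or 63 v 21 before the exclusion. Rejection rates are simulated (20,000 runs per cell).

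| f | r | Spurious benefit (ml) | Two-sided rejection |
|---|---|---|---|
| 15% | 0.1 | 0.36 | about 5% |
| 15% | 0.5 | 1.78 | about 9% |
| 16.7% | 0.1 | 0.39 | about 5% |
| 16.7% | 0.3 | 1.17 | about 6.5% |
| 16.7% | 0.5 | 1.95 | about 10% |
| 25.8% | 0.1 | 0.57 | about 5% |
| 25.8% | 0.3 | 1.70 | about 8% |
| 25.8% | 0.5 | 2.83 | about 14% |

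At f = 16.7% and r = 0.3, about 85% of the rejections favour the device.

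Setting d directly gives a similar picture. With d = 5 ml, rejection is about 6% (p = 15%) and 7% (p = 25.8%). With d = 10 ml it is about 8% and 12%. The r = 0.5 rows imply a large d: 1.95/0.167 = 11.7 ml and 2.83/0.258 = 11.0 ml, nearly one SD.

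**The alternative.** In the same simulation the complier-average estimate centres on zero. Its standard error is about 16 to 32% larger than the as-treated one. Per-protocol was not simulated separately.

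**The case against.** The strongest reply is that the plan's own planning assumption removes the bias. Protocol 6.6 takes non-implanted patients as "thus yielding regurgitant volume results similar to the Control group". If they have the Control mean, then implantable patients without a device have it too, d = 0, and as-treated is unbiased. This is correct, and it means the complier estimate cannot be justified by that assumption. The complier estimate rests on a different one: that a failed or unattempted implant does not itself change the 12-month outcome. It remains valid when d is not zero, which is the case that matters here.

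The size is also open. The model above treats every non-implant as a worst MR responder, and the correlation has no source in the documents. TITAN II, with the modified XE2 device, lists only access issues and coronary compromise, and the recapture rule in Protocol 3.7.1.2 names only safety grounds. If one third of non-implants were MR-driven (an assumption), rejection at r = 0.3 to 0.5 falls to about 5.8 to 6.1% at 16.7% non-implants and 5.7 to 6.8% at 25.8%. This stands as a limit on size. It does not make the comparison randomized, because Protocol 1.1 and 2.2 keep MR reduction among the conditions for release.

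A reader might infer that difficult anatomies are weeded out of the Treatment arm alone. For the most part the documents do not support that: Protocol 3.5.3.3 puts the coronary sinus venogram before randomization in both arms, so only problems first found at the attempt are one-sided. Protocol 1.1 describes a venous angiogram after randomization, and the two passages need to be reconciled.

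Finally, both sets are supportive and no primary conclusion rests on them. That is right.

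**Conclusion.** The point holds as a statement about what kind of comparison these are. As-treated and per-protocol remove failed attempts from one arm after randomization, partly on on-table MR response or coronary compromise. They are non-randomized and open to selection bias, most likely towards the device, because poor acute MR response is one of the grounds for not releasing an implant.

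The stronger reading, that these analyses are known to be biased towards the device by a given amount, is not supported. Direction depends on the sign of d, and size on an unsourced correlation and on the share of non-implants that are MR-driven. The illustrated range of 0.4 to 2.8 ml is 4 to 28% of the 10 ml design difference. Its upper end is close to a worst case, and at r = 0.1 the test keeps its 5% level.

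Nor does this exclusion put the ITT primary result in doubt. The SAP's ITT set has its own one-arm exclusion, of Treatment patients with no implant attempt, but that is a separate matter.

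**What to change.** In Protocol 6.2 and 6.9 and SAP 2.4.2 and 2.4.3:

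- For the continuous endpoints (regurgitant volume, six-minute walk distance, LV volumes), add a complier-average estimate: the difference by randomized group divided by the proportion of Treatment patients implanted, by two-stage least squares or with a bootstrap confidence interval. Non-compliance is one-sided, because Controls cannot receive the device before 12 months.
- Take numerator and denominator from the same patients. For example, assume 5% of Treatment patients stop before an attempt and 15% have a failed attempt. Among evaluable patients the implanted share is 80/95 = 84.2% and the difference is 11.7 × 0.842 = 9.85 ml. Dividing by 0.842 returns 11.7, but dividing by 0.80 gives 12.3, which overstates the effect.
- State the assumption as the exclusion restriction, and say that it differs from the Protocol 6.6 assumption about the Control mean.
- State a missing-data assumption for procedural screen failures, who leave at one month without a 12-month value.
- Keep as-treated and per-protocol as supportive, labelled non-randomized and reported without confirmatory p-values.

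The proposal gives no complier estimate for major adverse events or heart failure hospitalizations.

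The cost is SAP wording, one extra estimate per continuous endpoint, and a wider interval than as-treated (standard error about 16 to 32% larger in simulation). No new data are needed, since patients with a failed attempt are already followed to 12 months.

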### CONFIDENTIEL / CONFIDENTIAL

Toute reproduction ou distribution, totale ou partielle, de ce document, sans autorisation préalable de MedPass International est interdite.  
Reproduction and distribution of this document, in whole or in part, is strictly forbidden without prior authorization from MedPass International.

Assignment of patients to populations will be reviewed and approved by the sponsor before the database lock.

### 2.3.3. Protocol Deviations

On a case-by-case basis, all protocol deviations will be reviewed and will be classified as “minor” or “major” according to the possible impact expected on primary results.

Patients meeting at least one of the following major deviations may be excluded from the PP population:

- At least one eligibility criterion not fulfilled;
- Treatment different from the randomized group assignment;
- Unblinded assessor(s);
- Unblinded subject(s);
- Patient who received alternative or confounding therapies (e.g., CRT, transplant, stenting, etc.);
- Study Windows not respected

All protocol deviations other than those defined in this section will be considered as minor and will not lead to patient exclusion from the PP population.

### 2.3.4. Treatment/device groups

2 treatment groups will be defined:

- Treatment group (CARILLON);
- Control group.

## 2.4. Statistical Analyses

### 2.4.1. Patient Disposition and Follow-up

#### 2.4.1.1. Patient Populations, follow-ups and withdrawals

The number of patients present at each visit, as well as the reasons for study exit will be presented by population and treatment group as appropriate.

The corresponding average time of patients' follow-up will also be presented by population and treatment group as appropriate.

The repartition by site will also be presented.

#### 2.4.1.2. Protocol Deviations

The focus of protocol deviations description will be on major deviations as defined in section 2.3.3.

The total number of major deviations and the number of patients with at least one major protocol deviation and the corresponding percentages will be summarized on the ITT population and by deviation category.

Major as well as minor protocol deviations will be detailed in a patients' data listing.

